RNA as prognostic biomarkers in patients with acute coronary syndrome

Sponsor IRCCS POLICLINICO SAN DONATO

PI: [name]

Co-I: [name]

Introduction and Rational

Ischemic heart disease is the most frequent cause of death in the world and is the disease. heart disease, which has the highest incidence and prevalence in industrialised countries [1, 2]. It includes several. clinical pictures caused by anatomical and/or functional pathologies of coronary arterial vessels capable of. determine the development of myocardial ischemia. Within ischemic heart disease is possible. distinguish chronic and acute coronary syndromes. Acute coronary syndromes (ACS). include two main categories, distinguished on the basis of the electrocardiographic picture: - Acute coronary syndromes without persistent overshooting of the ST tract (NSTEMI. coronary syndromes - not ST elevation), which include myocardial infarction without above the ST tract vellement (NSTEMI) and unstable angina (AU); pathologically the syndromes. Coronary NSTEMI are characterized by the subocclusion of a vessel, with necrosis or ischemia of the. successor layers in case of NSTEMI or UA respectively.. - Acute coronary syndromes with persistent ST elevation (coronary syndromes. STE - ST elevation); physiopathology, are caused by a complete occlusion of a vessel which, in the absence of reperfusion, causes a full-thickness necrosis. In patients with NSTEMI coronary syndromes, therapy is guided by stratification of risk and is aimed primarily at facilitating the resolution of the thrombus and avoiding its evolution towards a thrombus occlusive, in addition to the control of the ischemic-anginal picture. It is therefore necessary to set promptly a drug therapy that includes an antiaggregant therapy (single or in association), an anticoagulant therapy and drugs that reduce myocardial oxygen demand (e.g. beta-blockers). Patients should then be subjected, with different timing depending on the estimated ischemic risk, coronarography and possible myocardial revascularization. All patients with STEMI should receive, unless contraindications, therapy Binding antifungal with acetylsalicylic acid and a P2Y12 inhibitor (Prasugrel or Ticagrelor). The addition of an anticoagulant (non-fractionated heparin, enoxaparina, fondaparinux, bivalirudin).The primary therapeutic goal in patients with STEMI, however, is the re-channeling of the vessel occluded as early as possible. This can be achieved by two types of treatment, one pharmacological (fibrinolysis) and one mechanical (primary angioplasty). Primary angioplasty (with stent implant) is the treatment of choice for reperfusion coronary because it is much more effective than thrombolysis in obtaining the reunalization of the vessel occluded.

Despite thrombolytic therapy, angioplasty (PCI) and progress in recent decades have significantly improved the prognosis of patients after a heart attack with or without increase in the ST tract, the overall mortality rate is 8% to one month and 12% a year after discharge [3]. It has also been estimated that, following a myocardial infarction, about 40% of STEMI patients and 30% of NSTEMI patients develop a remodelling of the left ventricle (VS) resulting in contractile dysfunction within 12 months [4, 5].

Previous studies Randomized clinicians identified a left ventricle ejection fraction (FEVS) < 45 as cut-off to define a left ventricular systolic dysfunction [6]. The development of a Left ventricular dysfunction is one of the largest independent predictors of mortality after heart attack myocardial [3, 7]. In contrast to patients with acute myocardial infarction, patients with AU, have a preserved FEVS (>60%), an excellent prognosis and a low rate of evolution towards ventricular dysfunction at one year (5-7%) [8]. The AU, characterized by ischemia in the absence of cardiomyocytic necrosis, with the advent of high sensitivity tests for the dosage of troponins thistle accounts for 10% of all ACS [8].

Many circulating proteins, such as Creatine Kinase (CK-MB), cardiac troponin measured with high sensitivity test (hs-cTn), type B Natriuretic Peptide (NT-proBNP), the binding protein fatty acids (H-FABP), lactate dehydrogenase (LDH) have been studied for their potential as biomarkers and used (hs-ctn and NT-proBNP) in the diagnosis and prognosis of dysfunction ventricular [7]. LV pathological remodeling is characterized at the molecular level by a alteration of the expression of different transcripts be they encoding (mRNA) or non-coding (ncRNA) [9, 10]. In particular, circulating RNA, present both in the plasma and within the cells blood, is highly stable and easily measurable even if present at very low concentrations.

In addition, the potential of circulating RNA for use as biomarkers has been known for some time cardiovascular [11-13].

Objective of the project

We propose to carry out an observational, prospective study that involves the evaluation of predictive circulating biomarkers of ventricular dysfunction (FE <45%) in patients with ACS. In particular our aim will be to check if there are transcripts circulating in the blood peripheral, coding or not for proteins (mRNAs or ncRNAs), differently modulated in patients with ACS (ACS_signature) submitted to PCI, distinguished on the basis of the evolution towards dysfunction ventricular. Our study will be based on transcriptomic analysis of the entire genome.

Objectives

Primary objective:

Detect circulating transcripts encoding proteins (mRNAs) or not (ncRNAs) (ACS_signature) predictive ventricular dysfunction in patients with ACS undergoing PCI.

Secondary objective:

Evaluate the association of the ACS_signature with possible adverse events at 12 months and its prognostic ability in the prediction of adverse events additional to the use of standard clinical parameters. Adverse events are defined: death from cardiovascular causes, re infarction, non-fatal stroke, new coronary revascularization, arrhythmias, development of heart failure and new hospitalizations for cardiovascular causes.

Study population

378 patients with a first episode of ACS (STEMI, NSTEMI and UA) will be recruited to PCI.

Criteria for Inclusion:

1. Age >18 years
2. ACS patients (first episode), defined according to ESC 2017 guidelines [14]
3. Indication for treatment of percutaneous revascularization
4. Informed consent to enrol in the study

Exclusion Criteria

1. Severe valvulopathy or other conditions requiring cardiac surgery
2. Previous cardiac surgeries including coronary bypass
3. Total chronic occlusion
4. Patients with known hypersensitivity or contraindication to one of the following drugs:
 - heparin
 - aspirin,

- clopidogrel,
 - ticlopidine,
 - sirolimus,
 - everolimus.
5. Any contraindication to medicated stent implantation (DES)
 6. Patients with previous documented myocardial infarction;
 7. FEVS <30% before PCI
 8. Patients in cardiogenic shock
 9. Patients with evolved STEMI (> 48 h from onset of symptoms/Q-waves to ECG) or undergoing to fibrinolysis
 10. Patients with known previous cardiomyopathy with FEVS < 40%
 11. Patients with malignant neoplasm or systemic disease with a "quoad vitam" prognosis less than 1 year
 12. Patients with known active infectious diseases;
 13. Patients who are unable to give valid informed consent at the time enlistment
 14. Pregnant women

Study design

This study, observational, prospective, monocentric will rely on the recruitment of patients consecutive with acute coronary syndrome (STEMI, NSTEMI) treated with angioplasty. I am 4 years and 6 months for recruitment and 12 months thereafter for completion of the follow-up, followed by a period of three months to complete the data analysis. Recruitment will be divided into two phases, functional to the subsequent molecular analysis: one of discovery and one of validation, partially overlapped temporally. Based on literature and experience data previous [5], we expect the number of patients who will develop ventricular dysfunction at 12 months from the PCI will be higher among the STEMI than the NSTEMI. A number of NSTEMI patients higher, so the number of patients who will develop ventricular dysfunction will be similar between these two groups. In addition, 100 patients diagnosed with AU, in which a low rate of evolution towards left ventricular dysfunction, will form a group of further control that will be tested after the validation phase, more relevant and homogeneous compared to healthy patients.

	MONTHS																																								
	1	2	3	4	5	6	7	8	9	10	11	12	13	14	15	16	17	18	19	20	21	22	23	24	25	26	27	28	29	30	31	32	33								

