1.1. RECLUTAMENTO - DISCOVERY																																									
1.2. FOLLOW UP - DISCOVERY																																									
2.1. RECLUTAMENTO - VALIDAZIONE																																									
2.2. FOLLOW UP - VALIDATION																																									
3.1. EXP ACTIVITY PROFILING: POTENTIAL ACS_SIGNATURE																																									

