3.2. EXP ACTIVITY VALIDATION: VALIDATED ACS_SIGNATURE																																									
3.3. CODE BROKEN, CORRELATIONS AND STAT ANALYSIS																																									

Assessments	Pre-procedure	Post-procedure (12-24 h)	6 months	12 months
Medical History*	X		X	X
Recruitment criteria	X			
Blood draw ACS_SIGNATURE	X	X	X	X
Blood count*	X	X	X	X
Blood draw Tn-hs e CK-MB*	X	X		
ECG*	X	X	X	X
Echocardiography *	X	X	X	X
Angiography *	X			
Endpoints			X	X

* routine clinical evaluations

Patients will be enrolled after diagnosis of ACS and before coronary surgery and will be treated according to the guidelines provided for the treatment of acute coronary syndrome and for post-PCI. Unless special contraindications, all patients will receive optimal medical therapy that includes:

- Dual therapy for 12 months
- Statins
- beta-blockers,
- ACE inhibitors,
- Mineralocorticoid receptor antagonists.

Follow-up visits including echocardiographic examination will be performed at 6 and 12 months from myocardial revascularization procedure. The evaluation of the FEVS will be carried out by 3D echocardiography that, as has been documented, shows a proven concordance with the MRI [15]. This method has also shown high reproducibility, with low intra- and inter-operator variability, and increased diagnostic accuracy. During the echocardiographic examination, in addition to FEVS data, other function indices will be evaluated systolic left ventricle such as, for example, telesistolic volumes, telediastolic, parameters tissue Doppler derivatives and myocardial strain indices (global Longitudinal strain).

The study will also need to take samples that will be made with the following scheme: 1) pre operative, before PCI, 2) post-operative 1 taken at 12 - 24h from PCI, 3) post-operative2 -6 months after PCI and 4) post-operative3-12 months after PCI.

Pre-operative withdrawal will be performed in the recovery room of the hemodynamics room after diagnosis of ACS. The post-operative withdrawal.1 will be performed at the Department of Cardiology 12/24 hours after the procedure. Post-operative.2 and post-operative.3 withdrawals will be performed outpatient during the planned echocardiographic checks (6 and 12 months respectively).

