RNA that will pass validation (Validated ACS_Signature), will be further tested also in the AU control group and all other timepoints, to assess the time trend potential biomarkers. In addition, the expression of the Validated ACS-Signature will be evaluated in the plasma and whole blood, to assess biodistribution and translational potential. Patient recruitment, withdrawals, patient data collection and all clinical procedures requests will be made by the Clinical, Interventional and Intensive Care Cardiology Unit Coronary Surgery (UTIC) of the IRCCS Policlinico San Donato. The collection and conservation of blood and pre-analytic treatment will be carried out at the BioCor Biobank of the IRCCSPoliclinico San Donato, while RNA measurements will be carried out in the Laboratory of Molecular Cardiology of IRCCS Policlinico San Donato. The study of modulated transcripts by RNA Sequencing with library preparation, sequencing and analysis bioinformatics will be carried out at the Center for Translational Genomics and bioinformatics, of the San Raffaele Hospital.

Sample size

Based on literature [4, 5] it is expected that about 40% of STEMI patients and 30% of STEMI patients NSTEMI patients, after a first episode of myocardial infarction, experience dysfunction of the left ventricle.

Based on these data, we expect recruiting in 18 months 278 patients with ACS performing PCI, 100 will experience ventricular dysfunction (Table 1).

Table 1. Patient recruitment and follow up				
Study phase	Total number of patients		Dysfunction LV expected	
	STEMI	NSTEMI	STEMI	NSTEMI
DISCOVERY	49	75	20	22
VALIDATION	61	93	31	28
TOTAL STEMI + NSTEMI	110	168	50	50

The number of patients to be recruited will be 378, of which 110 STEMI, 168 NSTEMI and 100 AU, as control. By preventing 100 events in total, respectively 50 per group, you can enter about 6/7 variables for each model of multivariate logistic regression (STEMI NSTEMI). Experimental RNA measurement activities shall follow the distribution shown in Table 2.

Table 2. Experimental activity				
	DISCOVERY		VALIDATION	
	STEMI	NSTEMI	STEMI	NSTEMI
LV DYSFUNCTION	20	20	50	50
NO LV DYSFUNCTION	20	20	60	118
TOTAL	40	40	110	168

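### Does stating recruitment as 4 years 6 months in one place and 18 months in another call for a change to the plan?

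*Protocol*

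**What the plan says.** The protocol (Study design) describes a single-centre prospective cohort of "patients consecutive with acute coronary syndrome (STEMI, NSTEMI) treated with angioplasty". It then gives the timetable as "I am 4 years and 6 months for recruitment and 12 months thereafter for completion of the follow-up", with a further three months for analysis. The next sentence reads "Recruitment will be divided into two phases, functional to the subsequent molecular analysis: one of discovery and one of validation", and notes that the two phases partly overlap in time. Later in the same paragraph the 100 unstable-angina patients are added as a further control group, to be tested after validation. No dates are given for them.

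The month chart in that section is numbered 1 to 33. Its seven rows run from discovery recruitment through "2.1. RECLUTAMENTO - VALIDAZIONE" to "3.3. CODE BROKEN, CORRELATIONS AND STAT ANALYSIS". None names unstable angina.

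Under Sample size the protocol says "we expect recruiting in 18 months 278 patients with ACS performing PCI". Below Table 1 it gives the full target: "The number of patients to be recruited will be 378, of which 110 STEMI, 168 NSTEMI and 100 AU, as control". The Introduction says of unstable angina that it "accounts for 10% of all ACS".

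**The concern.** The two recruitment periods differ threefold and seem to describe the same patients. The longer one is followed at once by the split into discovery and validation, and Table 1 fills those two phases with the 278 STEMI and NSTEMI patients only. Those are the patients the Sample size section expects within 18 months.

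If both statements bind, the document gives no single date for the end of follow-up, the code break or the final analysis, and the accrual the centre must sustain is unclear. The controls add a second doubt. At a 10% share of acute coronary syndromes, enrolling them only alongside 278 infarct patients would yield far fewer than 100. A reader could conclude that the target of 378 has not been shown to be feasible.

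**Working it through.** **Inputs.** Study design: recruitment of 4 × 12 + 6 = 54 months, then 12 months of follow-up and 3 of analysis; chart numbered to 33. Sample size: 18 months for 278 patients; targets of 110, 168 and 100. Introduction: unstable angina as 10% of acute coronary syndromes. The chart's bars are not visible in the text at hand, so only its numbering and row labels are used.

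**1. Reproducing the chart.** Total length = recruitment + 12 + 3.
- 18 + 12 + 3 = 33, equal to the last numbered month.
- 54 + 12 + 3 = 69, which is 69 − 33 = 36 months beyond it.
- Follow-up ends at 18 + 12 = 30 or at 54 + 12 = 66.

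The chart and the Sample size section agree with each other. The 54-month figure stands alone.

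**2. Are these the same patients?** Table 1 gives 49 + 75 = 124 for discovery and 61 + 93 = 154 for validation, and 124 + 154 = 278 = 110 + 168. Adding 100 gives 378. The 18 months is thus tied to the 278. The 54 months can be read as covering the same 278, or as the window for the whole study of 378.

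**3. Implied accrual per month.**

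| Patients | Over 18 months | Over 54 months |
|---|---|---|
| 278 | 278/18 = 15.4 | 278/54 = 5.1 |
| 378 | 378/18 = 21.0 | 378/54 = 7.0 |

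**4. Unstable-angina numbers.** If a share *s* of the intake has unstable angina and the other patients number 278, the expected count is 278 × *s*/(1 − *s*).
- *s* = 5%: 14.6. *s* = 10%: 30.9. *s* = 25%: 92.7.
- Reaching 100 needs *s* = 100/378 = 26.5%.
- If infarct patients present at 15.44 a month throughout, a 10% share gives 15.44 × 0.1/0.9 = 1.72 controls a month. That is 92.7 in 54 months, and 100 in about 58 months.

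These results carry little weight. The 10% refers to all acute coronary syndromes, not to first-episode patients referred for PCI at one centre. The formula treats 278 as a natural intake, but the Study design section sets the NSTEMI number higher on purpose, so that dysfunction counts are similar in the two groups. The last line also takes its rate from one disputed statement and its duration from the other.

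**5. What uses the recruitment length?**
- Sequencing power (94%): 20 patients per group, 17,500 tests, 40 transcripts, FDR 0.02. No time term.
- qPCR power (95%): 50 per group, 2.2-fold difference, α = 0.01, σ = 1.4. No time term.
- Regression models: 50 expected events each in STEMI and NSTEMI. These follow from patient numbers and dysfunction rates.
- Outcomes: ventricular function and adverse events at 12 months, timed from each patient's own procedure.
- Unstable-angina group: tested only after validation. No power statement rests on its 100.

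Every item is the same whether recruitment takes 18 or 54 months.

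**The case for a change.** The strongest case for acting is that recruitment period and accrual belong in the protocol itself and cannot be left to an analysis plan. This protocol states the period twice and disagrees with itself, and the chart sides with the shorter one. Reading the 54 months as a wider window that takes in the controls is not supported by any sentence, and a chart numbered to 33 could not display it. Sequencing also waits for the discovery patients' outcomes, so the laboratory timetable moves with the choice.

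Most of this stands as description. The text is inconsistent, and it does not show which period was intended. Two parts do not stand.
- It is too strong to say that the two periods cannot both be true. The 18 months is worded as an expectation for a subset, and a forecast can be shorter than the time allotted.
- The controls are part of the 378 and so fall, by default, within the study's recruitment period. Nothing obliges a protocol to give a separate window, rate or chart row for each group.

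The laboratory timetable does move, but which patients are sequenced depends on their outcomes and not on the date. A longer recruitment could let treatment practice or laboratory batches drift. Correcting a date in the text would not prevent that.

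**Conclusion.** This is a timeline slip of 36 months (33 against 69 in total) with no consequence for inference. Sample size, expected events, power, endpoints and analyses are unchanged under either duration, so reconciling the wording would not alter any conclusion the study can draw. The accrual rates can be worked out under both statements (21.0 or 7.0 a month for all 378), so feasibility can be judged by anyone who knows the centre's volume. Separate rates and chart rows for each group would only write down operational detail.

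This rests on two assumptions. The first is that enrolment runs to the stated numbers; the protocol gives those numbers and no rule that ends recruitment on a date. The second is that the 12-month assessment stays tied to each patient's procedure, as the follow-up schedule states. If the unstable-angina group fell short, the comparison of patients with and without dysfunction among STEMI and NSTEMI would be untouched. The wording and chart can be aligned at a routine edit, and the plan itself needs no change.

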1.1. RECLUTAMENTO - DISCOVERY																																									
1.2. FOLLOW UP - DISCOVERY																																									
2.1. RECLUTAMENTO - VALIDAZIONE																																									
2.2. FOLLOW UP - VALIDATION																																									
3.1. EXP ACTIVITY PROFILING: POTENTIAL ACS_SIGNATURE																																									
3.2. EXP ACTIVITY VALIDATION: VALIDATED ACS_SIGNATURE																																									
3.3. CODE BROKEN, CORRELATIONS AND STAT ANALYSIS																																									

Assessments	Pre-procedure	Post-procedure (12-24 h)	6 months	12 months
Medical History*	X		X	X
Recruitment criteria	X			
Blood draw ACS_SIGNATURE	X	X	X	X
Blood count*	X	X	X	X
Blood draw Tn-hs e CK-MB*	X	X		
ECG*	X	X	X	X
Echocardiography *	X	X	X	X
Angiography *	X			
Endpoints			X	X

* routine clinical evaluations

Patients will be enrolled after diagnosis of ACS and before coronary surgery and will be treated according to the guidelines provided for the treatment of acute coronary syndrome and for post-PCI. Unless special contraindications, all patients will receive optimal medical therapy that includes:

- Dual therapy for 12 months
- Statins
- beta-blockers,
- ACE inhibitors,
- Mineralocorticoid receptor antagonists.

Follow-up visits including echocardiographic examination will be performed at 6 and 12 months from myocardial revascularization procedure. The evaluation of the FEVS will be carried out by 3D echocardiography that, as has been documented, shows a proven concordance with the MRI [15]. This method has also shown high reproducibility, with low intra- and inter-operator variability, and increased diagnostic accuracy. During the echocardiographic examination, in addition to FEVS data, other function indices will be evaluated systolic left ventricle such as, for example, telesistolic volumes, telediastolic, parameters tissue Doppler derivatives and myocardial strain indices (global Longitudinal strain).

The study will also need to take samples that will be made with the following scheme: 1) pre operative, before PCI, 2) post-operative 1 taken at 12 - 24h from PCI, 3) post-operative2 -6 months after PCI and 4) post-operative3-12 months after PCI.

Pre-operative withdrawal will be performed in the recovery room of the hemodynamics room after diagnosis of ACS. The post-operative withdrawal.1 will be performed at the Department of Cardiology 12/24 hours after the procedure. Post-operative.2 and post-operative.3 withdrawals will be performed outpatient during the planned echocardiographic checks (6 and 12 months respectively).

In pre-operative and post-operative samples.1 the complete blood count will be performed and Tn-hs, NT-proBNP and LDH will be dosed RNA analysis will be divided into two phases: in the discovery phase, the analysis of the transcriptome by RNA sequencing. The aim is to identify a potential ACS_signature in blood mononucleate cells (PBMCs) of a subset of patients who eventually of the follow up of the discovery phase, show ventricular dysfunction (n= 40) or function conserved ventricular (n= 40). An equal number of STEMI and NSTEMI patients will be analysed.

In the validation phase, the ACS_signature will be measured with independent technique (qPCR) in all patients enrolled in the study, to obtain a Validated ACS-Signature.

Study procedures

They will be taken at each time-point: 1) 3 ml of whole blood in a tube containing stabilizers RNA (type PAX-gene or Tempus), 2) 4 ml in a tube containing EDTA from which the plasma that will be frozen at -80,5° C pending the extraction of RNA, and 3) 4 ml in a tube containing EDTA from which PBMCs will be isolated. The withdrawals in point 2 and 3 must be processed within two hours of the withdrawal, while the withdrawal in tube with RNA stabilizer can be stored at room temperature for up to 3 days, at +4 killed C for 7 days and at -20 killed C/-80 killed C indefinitely without altering the integrity of nucleic acids. Plasma and whole blood RNA will be extracted by silica columns, while RNA from PBMCs will be extracted by Trizol. The integrity of the extracted RNA will be evaluated by running on capillary gel type Bioanalyzer.

On RNA extracted from PBMCs derived from pre-operative sampling in the discovery group, it will be analysis of the entire transcriptome by RNA sequencing (platform Illumina), in order to identify a potential ACS_signature consisting of transcripts differentially expressed in the two groups of patients: those with left ventricular dysfunction and those without ventricular dysfunction.

In the validation phase, the potential ACS_signature will then be validated by qPCR in all STEMI and NSTEMI patients enrolled in the study, including those who will submit a degree intermediate ventricular dysfunction (LVEF 45-49%). They will also be analysed separately two subgroups of patients diagnosed with STEMI and NSTEMI.

RNA that will pass validation (Validated ACS_Signature), will be further tested also in the AU control group and all other timepoints, to assess the time trend potential biomarkers. In addition, the expression of the Validated ACS-Signature will be evaluated in the plasma and whole blood, to assess biodistribution and translational potential. Patient recruitment, withdrawals, patient data collection and all clinical procedures requests will be made by the Clinical, Interventional and Intensive Care Cardiology Unit Coronary Surgery (UTIC) of the IRCCS Policlinico San Donato. The collection and conservation of blood and pre-analytic treatment will be carried out at the BioCor Biobank of the IRCCSPoliclinico San Donato, while RNA measurements will be carried out in the Laboratory of Molecular Cardiology of IRCCS Policlinico San Donato. The study of modulated transcripts by RNA Sequencing with library preparation, sequencing and analysis bioinformatics will be carried out at the Center for Translational Genomics and bioinformatics, of the San Raffaele Hospital.

Sample size

Based on literature [4, 5] it is expected that about 40% of STEMI patients and 30% of STEMI patients NSTEMI patients, after a first episode of myocardial infarction, experience dysfunction of the left ventricle.

Based on these data, we expect recruiting in 18 months 278 patients with ACS performing PCI, 100 will experience ventricular dysfunction (Table 1).

Table 1. Patient recruitment and follow up				
Study phase	Total number of patients		Dysfunction LV expected	
	STEMI	NSTEMI	STEMI	NSTEMI
DISCOVERY	49	75	20	22
VALIDATION	61	93	31	28
TOTAL STEMI + NSTEMI	110	168	50	50

The number of patients to be recruited will be 378, of which 110 STEMI, 168 NSTEMI and 100 AU, as control. By preventing 100 events in total, respectively 50 per group, you can enter about 6/7 variables for each model of multivariate logistic regression (STEMI NSTEMI). Experimental RNA measurement activities shall follow the distribution shown in Table 2.

Table 2. Experimental activity				
	DISCOVERY		VALIDATION	
	STEMI	NSTEMI	STEMI	NSTEMI
LV DYSFUNCTION	20	20	50	50
NO LV DYSFUNCTION	20	20	60	118
TOTAL	40	40	110	168

For discovery activities using RNA-sequencing, based on literature data [16], we assume a sample size of 40 patients (20 per group) to evaluate the 40 transcripts that differentiate patients with ventricular dysfunction and not ventricular dysfunction, out of a total of 17,500 tests, considering a power of 94.0 %, a value of FDR equal to 0.02. For the activities of validation using qPCR, 95% power is obtained by analyzing 50 samples per group evaluating differences between the averages of 2,2 times, with $\alpha=0,01$ and $\sigma=1,4$.

Statistical methods

The characteristics of patients will be presented with the average, median, standard deviation and range interquartile for continuous and frequency variables and % for nominal and categorical variables. The Shapiro-Wilks will be used to check if distributions are Gaussian. For distributions normal, statistical analysis will be carried out with parametric tests while for non-normal distributions a non-parametric statistical analysis will be carried out. Logistic regression models will be used to assess the association between gene characteristics and clinical outcome. In particular, the power discriminatory (c statistics) will be expressed in terms of area under the curve in a Receiver Operating Characteristics (ROC) analysis. Different cut-off levels will be explored for each of which sensitivity, specificity, negative predictive power and positive predictive power will be evaluated. The added prognostic value of ACS_signature in relation to variables will also be assessed traditional clinics including NTproBNP, Tn-hs and CK-MB using the prediction curve.

Ethical aspects

The study will be conducted according to GCP, local laws and rules of the World Medical Association Declaration of Helsinki.

Publication policy

The data collected are the property of IRCCS Policlinico San Donato and will be the subject of publication.

Bibliography

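### The qPCR validation set of 278 includes the 80 sequenced patients who select the transcripts, so it is independent in technique but not in patients

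*Protocol*

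**What the plan says.** The Study design section of the Protocol states: "Recruitment will be divided into two phases, functional to the subsequent molecular analysis: one of discovery and one of validation". Table 1 (Sample size) gives each phase its own patients. Discovery has 49 STEMI and 75 NSTEMI; the validation row reads "VALIDATION 61 93 31 28", that is, 61 STEMI and 93 NSTEMI with 31 and 28 expected dysfunction cases.

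The analysis set for validation does not follow that split. The end of Study design says that "the ACS_signature will be measured with independent technique (qPCR) in all patients enrolled in the study". Study procedures repeats it for the infarction groups: "the potential ACS_signature will then be validated by qPCR in all STEMI and NSTEMI patients enrolled in the study". Table 2 agrees; its total row is "TOTAL 40 40 110 168", so validation covers all 110 STEMI and 168 NSTEMI patients.

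The transcripts are selected by sequencing pre-procedure PBMC RNA in 40 discovery patients with dysfunction and 40 without. The planning figures are "a value of FDR equal to 0.02" for discovery and, for qPCR, "95% power is obtained by analyzing 50 samples per group".

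**The concern.** The 80 sequenced patients come from the discovery cohort, so all of them lie inside the 278, and no sentence removes them from validation. The only independence claimed is that of the assay.

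A second assay can remove measurement error in the sequencing. It cannot remove the chance imbalance between those 40 cases and 40 non-cases that made a transcript look different. Other timepoints, plasma and whole blood are deferred until after validation, so the validation appears to re-measure the same timepoint and cell compartment in these patients.

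Two things are at stake. A falsely selected transcript passes validation more often than the nominal rate. For true transcripts, the effect size, the c-statistic and the cut-offs with their sensitivity and specificity are optimistic if computed on the same 278. The validated signature then feeds the unstable angina comparison, the time-trend analysis and the added-value analysis.

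**Working it through.** **1. Size of the overlap (Tables 1 and 2).**
- All: 80/278 = 29% of patients; 40/100 = 40% of cases.
- STEMI: 40/110 = 36%. NSTEMI: 40/168 = 24%. In each, 20 of 50 cases.

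**2. The plan's own power figure.** Inputs from Sample size: 2.2-fold difference, SD 1.4, alpha 0.01, 50 per group. The scale and sidedness are not stated, so I use a two-sided two-sample t-test on two scales.
- log2 scale: d = log2(2.2)/1.4 = 1.1375/1.4 = 0.81; power 0.922.
- Raw scale: d = (2.2 − 1)/1.4 = 0.857; power 0.949, which reproduces the stated 95%.

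**3. Pass probability for a false transcript.** Under the null, the discovery z (n per arm = m) and the full-sample z (a cases, b non-cases) have correlation r = √[(1/a + 1/b)/(2/m)].
- Pooled: √[(1/100 + 1/178)/(2/40)] = 0.559.
- STEMI: √[(1/50 + 1/60)/(2/20)] = 0.606.
- NSTEMI: √[(1/50 + 1/118)/(2/20)] = 0.534.

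Multiply r by the sequencing/qPCR correlation, which the Protocol does not give and which I assume to be 0.6–1.0. Given discovery z = 4, the full-sample z is normal with mean 4r and variance 1 − r². P(|z| > 2.576) is then:

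| Assumed correlation | Pooled 278 | New patients |
|---|---|---|
| 0.6 | 0.095 | 0.01 |
| 0.8 | 0.189 | 0.01 |
| 1.0 | 0.341 | 0.01 |

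If selection and validation are both done within a stratum, the range is 11–42% in STEMI and 9–30% in NSTEMI. A separate null simulation with weaker selection (top 40 of 17,500) gave about 4%, 10% and 19% at correlations 0.5, 0.8 and 1.0, against about 1% in unsequenced patients.

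**4. Simulation at the planned FDR.** 17,500 independent transcripts, 40 true; Benjamini-Hochberg at 0.02 in 40 v 40; then p < 0.01 in the overlapping 100 v 178 or in an independent 52 v 102; 500 studies per effect size; correlations 0.6–1.0.
- d = 0.81: 90 false transcripts selected in total (0.18 per study). With overlap 11, 15 and 42 of the 90 pass (12–47%); in independent patients 0–1 pass. Mean single-transcript AUC 0.726–0.739 against 0.709–0.710; effect size 8–14% too large.
- d = 0.65: AUC 0.693–0.714 against 0.667–0.673.
- d = 1.25: 404 false selected (0.81 per study). With overlap 51, 91 and 137 pass (13–34%); in independent patients 2–5 pass. AUC 0.808–0.810 against 0.805.

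**5. Power without the discovery patients** (the 154; two-sided t, alpha 0.01; d = 0.81 / 0.857). Two case counts are needed because Table 1 gives 31 STEMI cases of 61 (51%), whereas the stated 40% gives about 24.

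| Analysis | Cases v non-cases | Power |
|---|---|---|
| Pooled | 52 v 102 | 0.984 / 0.992 |
| Pooled | 59 v 95 | 0.988 / 0.994 |
| STEMI | 24 v 37 | 0.669 / 0.726 |
| STEMI | 31 v 30 | 0.694 / 0.751 |
| NSTEMI | 28 v 65 | 0.830 / 0.874 |

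The pooled analysis has more than 50 cases without any re-use. Only the separate strata need the discovery cases to reach 50.

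**6. Model size.** Fifty events with 6 to 7 variables is 50/7 = 7.1 to 50/6 = 8.3 events per variable. With 24–31 STEMI or 28 NSTEMI events, the same ratio allows 24/8.3 = 2.9 to 31/7.1 = 4.3, about 3–4 variables.

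**The case against.** The overlap itself is not in dispute; its size is. Discovery is planned at 94% power with FDR 0.02. At d = 0.81 and d = 0.65, discovery power in the simulated design is only about 14% and 2%, so the larger optimism figures describe studies in which discovery has mostly failed. At d = 1.25 (about 88% power) the AUC is inflated by no more than 0.005, and about 0.81 × 13–34% = 0.1–0.3 false transcripts are validated per study. This stands: if discovery performs as planned, the harm is small. But d = 0.81 is what the Protocol's own qPCR assumptions give on the log2 scale, so the moderate case cannot be set aside.

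It is also fair that alpha 0.01, like FDR 0.02, appears only as a planning input, and that no pass criterion for validation is stated. The pass rates are therefore conditional on using 0.01, on the transcript having been falsely selected, and on an assumed assay correlation.

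The Statistical methods section names no analysis set for the ROC and cut-off work, and a SAP could add an optimism correction. That weakens the point for those estimates, but not for validation itself: two sentences and a table fix that set at all enrolled STEMI and NSTEMI patients.

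Finally, all 278 can still be measured, and results in them can be shown alongside. That is compatible with the change below, provided they are not called validation.

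**Conclusion.** The concern holds. As written, 80 of the 278 validation patients, with 40 of the 100 expected cases, also select the transcripts, so the signature is not validated in independent patients. This structural error depends on no assumption and must be corrected.

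Its numerical effect does depend on assumptions: independent transcripts, a sequencing/qPCR correlation of 0.6–1.0, and a 0.01 pass rule. Under these, a false transcript selected at z = 4 passes 10–34% of the time instead of 1%. If FDR 0.02 is the actual selection rule and holds, fewer than about one false transcript per study is expected, and optimism in effect size and AUC is the main harm: about 0.02–0.04 in AUC at moderate effects, near zero at large ones. Re-use is not needed for pooled power.

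**What to change.** - State that the confirmatory qPCR test and all performance estimates use only patients who were not sequenced, preferably the 154 in Table 1's validation row.
- The 124 − 80 = 44 unsequenced discovery patients may be added for transcript-level tests. They are what remains after selection by outcome (about 42 − 40 = 2 cases and 42 non-cases), so they would distort predictive values and should stay out of those.
- Report qPCR in the 80 sequenced patients as technical concordance only.
- Correct Table 2's validation columns to match. First reconcile Table 1: 31 STEMI cases of 61 conflicts with the stated 40%, and 20 + 31 = 51, not the 50 shown.
- Restate power for the pooled and separate analyses, with scale and sidedness. Revise the statement that "you can enter about 6/7 variables for each model of multivariate logistic regression" to about 3–4 per stratum model.

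The cost is wording, one table and restated power, with no new patients or assays. Pooled power stays above 95%. The real price is that the separate STEMI and NSTEMI analyses no longer reach the stated 95% and their models must be smaller.
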